## SUMMARY

Promotor	INRA
Main investigator	[name]
Co-Investigators	[name], [name], [name]
Title	Identification of new biomarkers of banana and tomato intake
Rational	In epidemiological studies, dietary intakes are assessed by questionnaires, an approach with inherent limitations associated with self-reporting : memory bias, difficulty to estimate portion size, insufficient coverage of the dietary diversity... The use of biomarkers of food intake should markedly improve the accuracy of dietary assessment, However, only few validated biomarkers are available. A large European project (FoodBALL) was funded by the JPI HDHL to identify a large range of new biomarkers of intakes, using untargeted metabolomics on urine and plasma samples collected in a series of controlled nutritional intervention studies.
Objective	The BioBanaTom study aims, in the framework of the FoodBALL project, at identifying new biomarkers of intake for banana and tomato, two important foods of the European diet.
Evaluation criteria	Main Criteria: Identification using metabolomics of plasma and urine metabolites specifically associated to banana and tomato intake, for validation as biomarkers. Secondary criteria : Obtention of reference metabolomics profiles which may be related to metabolic impact of an acute intake of tomato or banana.
Methodology	Cross-over randomized, open, controlled
Number of subjects	12
Undesirable effects	No undesirable effect expected beyond those link to blood sampling (small local hematoma, slight local inflammation)
Recruitment modalities	Volunteer file of UEN declared to the CNIL, mailing CHRU and INRA Clermont-Ferrand-Theix, local medias. The selection of the volunteers will be performed during medical inclusion visits.
Main selection criteria	Inclusion criteria Men and women, healthy (normal medical and biological exam), non-smoking, aged 18 to 40, BMI>18,5 and <30 kg/m  , with no aversion for banana or tomato. Exclusion criteria Smokers, diagnosed with infectious or chronic disease, under medication (except contraception pill), having followed an antibiotic treatment in the last 3 months, consuming dietary supplements several times a week, pregnant and lactating women, vegetarian as the protocol implies consumption of standardized meal containing meat.
Protocol description	Written consent will be obtained after complete information of the subjects about the objectives, and the nature and possible risks of the study (informed consent form in duplicate, one copy given to the volunteer). The protocol will be explained in details, with objectives and constraints, according to the information form, by the scientist in charge. A clinical exam and a check-up of all selection criteria will be performed by the main investigator or another medical doctor.  At the inclusion visit, subjects will have a medical exam including questionnaire

	
regarding past medical history, family background, medical treatments and standard clinical exam (weight, height, blood pressure) and a blood sampling. A food frequency questionnaire will also be completed. The conformity to the selection criteria will be checked during this medical exam. The selected subjects will be definitely included after validation of the selection criteria by the investigator.
 
The volunteers will consume in 3 distinct experimental periods either a control drink (oral nutritional complement Fresubin, 250 mL), or 240g banana (and 150 ml Fresubin), or 300g tomato (with 12 g sunflower oil and 150 mL Fresubin). Every volunteer will consume the 3 test foods, in a randomized order. After test food intake, urine will be collected over 24h in 7 fractions. Blood samplings will be performed before the food consumption (t0) and in post-prandial period (4 samplings at 1h, 2h, 4h et 6h), as well as on the following day in fasting state (t24h). the volunteers will follow a tomato and banana-free diet during the study days, as well as a more restrictive diet, without plant-based food, on the sampling days and on the day before. A 24h recall will be filled for the dietary intakes on the day before the sampling days (D2).
 
Samples will be analyzed using an untargeted metabolomics approach (LC-MS, GC-MS et RMN) with the aim to identify new biomarkers of tomato and banana intake.
 
The total volume of sampled blood will be 154 ml per subject.

Duration	
Duration of the study for every volunteer : 8 weeks
 
Total duration of the study: 6 months for the subject selection and realization of all experimental periods for all the volunteers
 
Total duration of the project : 3 years

Indemnities	350€ per subject
Duration of exclusion	The exclusion duration for the participation of the volunteer to another study is fixed at 1 month.
Location of the study realization	
Centre de Recherche en Nutrition Humaine d’Auvergne
 
Unité d’Exploration Nutritionnelle
 
[name]
 
Agrément pour la Recherche Biomédicale n°2012 - 476

Funding	This study is part of an international research project: Project FoodBall, JPI HDHL 2015-2017.

## **LIST OF ABBREVIATIONS**

ANSM : Agence Nationale de Sécurité du Médicament

CPP : Comité de Protection des Personnes

CRNH : Centre de Recherche en Nutrition Humaine d’Auvergne

INRA: Institut National de Recherche Agronomique

JPI HDHL: Joint Programing Initiative Healthy Diet for Healthy Life

FoodBALL : Food Biomarker Alliance project

LC-MS = Liquid Chromatography- Mass spectrometry

GC-MS = Gas chromatography-Mass spectrometry

RMN or NMR : Nuclear Magnetic Resonance

## 1 – GENERAL INFORMATION

### 1-1 STUDY TITLE

Identification of new biomarkers of banana and tomato intake

### 1-2 STUDY IDENTIFYING NUMBER AND DATE

Study identifying number	Type
JPI HDHL 2015-2017 2016-A00153-48	European Number IDRCB CPP
BioBanaTom	Acronym

## 2 – INTRODUCTION AND RATIONALE

Determining dietary exposure is a challenging endeavor in nutritional research. The most common tools used in dietary assessment are based on self reporting methodology such as 24-hour recall questionnaires, food frequency questionnaires and weighted dietary records. However, the information obtained through these tools may not be entirely reliable since they depend on the individual's memory and honesty which compromises the objectivity of the dietary assessment. Through the identification of dietary biomarkers in biological fluids, nutritional researchers have found a more objective way to determine dietary exposure. A dietary biomarker may be defined as a specific measurement in a biological sample that accurately reflects the intake of a specific food or food constituent. By knowing how foods are metabolized the possibility of identifying unique biomarkers for each food or food groups is possible.

There are many factors that influence biomarkers of intake discovery; individual's characteristics such as genetic variants, environmental factors, food matrix and the lifespan of the compound may change the metabolites identified in biofluids. Another key factor for discovery of biomarkers of intake is the nature of the biological sample, where accessibility plays an important role. Urine and plasma are easy access biofluids and therefore, they are the main biological sources used to assess metabolites of intake in different studies.

The rise of metabolomics along with different platforms such as liquid chromatography mass spectrometers (LC-MS), have allowed the assessment of thousands of metabolites simultaneously in biological samples and the recognition of patterns that may constitute a fingerprint of the intake of different foods. Recent studies demonstrated the great potential of metabolomics to discover new biomarkers of intake in intervention and cohort studies.

The diversity of compounds found in food metabolomics represents a major challenge and so in an international effort to improve dietary biomarkers identification and validation, the Food Biomarkers Alliance (FOODBALL) has been created. In this project, 22 institutions from 11 different countries will collaborate in three main tasks: 1) Discovery of new dietary biomarker using a metabolomic approach, 2) systemic validation of existing and newly discovered biomarker to achieve a good coverage of food intake in different European populations and 3) exploring biological effects using biomarkers of intake (<http://foodmetabolome.org/>). With the latter, the necessity of building a chemical library that allows the use of standards for further identification arises. Along with FOODBALL, The Food Compound Exchange (FoodComEx) aims to improve availability of analytical standards of biological compounds to achieve a better and easier biomarker identification (<http://foodcomex.org/>).

As part of INRA collaboration to FOODBALL and FoodComEx, the present project attempts to identify biomarkers of banana and tomato intake, through the exploration of the serum and urine metabolome of subjects who consumed these foods in a controlled intervention. The same study design will be applied in six different centers within Europe to assess biomarkers of the intake of 12 public health related foods.

Tomatoes were introduced to European countries in the 16th century. The origin of tomatoes may be tracked back to the Aztec civilization in Mexico. There are fifteen leading countries in the production of tomato China, US, India, Turkey, Egypt, Italy, Spain, Brazil, Iran, Mexico, Greece, Russian Federation, Ukraine, Chile and Uzbekistan which supports the fact that tomatoes are between the five most eaten vegetables in the world. Tomatoes contain a large variety of micronutrients ( $\beta$ -carotene as pro-vitamin A, vitamin C, folate, and potassium) and other chemical compounds, including lycopene and polyphenols that are considered beneficial for health. Most of the published work on tomato is mainly focused on the association between the intake of lycopene and flavonoids, such as naringenin and hesperetin, and a lower risk for chronic diseases and cancer, however

lycopene and flavonoids are not robust exposure biomarkers of tomato intake for various reasons (low concentrations, interindividual variation in intestinal absorption and metabolism). Tomato contains many other phytochemicals that could be revealed as exposure biomarkers or bioactive compounds contributing to the health effects of tomato.

On the other hand, bananas (*musa spp*) are among the world's leading food crops as a source of energy, mainly in tropical regions. The use of pulp and peel of the banana as medicine remedies has been documented in traditional medicine in different continents such as Africa and America. The dietary recommendations for banana intake are based mainly in their content of pro-Vitamin A compounds such as trans- $\alpha$  and trans- $\beta$  carotenes and in their energy contribution. Like tomatoes, there are no validated exposure biomarkers on the literature.

Determining biomarkers of intake of banana, tomato and different other public health related foods will allow a more precise dietary assessment in nutritional epidemiology, opening the possibility of better investigating the health effects of foods and dietary patterns. Biomarkers will also be very useful to monitor compliance in controlled intervention studies.

### **3 – OBJECTIVES**

The overall aim of the project is to identify potential novel biomarkers of intake of tomato and banana in urine and blood of volunteers after acute consumption of these foods.

#### **3-1 PRIMARY OBJECTIVE OF THE CLINICAL STUDY**

The primary objective, within the FOOTBALL project, of the present study is to identify biomarkers of food intake after an acute dietary intervention with banana, tomato and a control drink on 12 healthy subjects, by comparing the metabolomic profiles analyzed for urine and serum samples collected over 24h.

#### **3-2 SECONDARY OBJECTIVES OF THE CLINICAL STUDY**

The secondary objectives of the BioBanaTom project are:

1. Collect reference urine and serum samples and associated metabolomic profiles after acute intake of banana and tomato to be shared in the FoodComEx library for analytical purposes.
2. Explore the modifications in metabolomics profiles that may be associated with metabolic effects of acute consumption of tomato and banana.

[figure not shown]
### **4 – PROTOCOL DESCRIPTION**

The present project is a randomized, controlled, crossover study with 12 subjects. A cross-over design has been selected as each subject can serve as his/her own control thereby minimizing variations. Limitations attributed to cross-over designs are possible order or carry-over effects. These effects will however be minimized due to a randomized intervention order. The study design does not allow blinding as intervention is the ingestion of different foods.

In this study, we will assess the metabolomic profiles of human biofluids after consumption of two different foods: banana (240g peeled fruit) and tomato (300g fresh fruit) in order to identify novel biomarkers for each food. As a control diet, a high energy high protein drink, Fresubin ® 2kcal fiber (Fresinius kabi) will be used. As shown in the general study plan, the intervention comprises three dietary intervention periods of 4 days each for each food of interest and the control drink. Each

intervention period will be separated by a washout period of minimum 3 days (and maximum 10 days). Volunteers will be randomly assigned to a different food at each time point. Volunteers will be asked to maintain their normal physical activity and follow the dietary recommendations between intervention periods; they will receive an information form containing the description and objectives of the project, and detailed instructions. A volunteer’s booklet will also include simple information about nutritional metabolomics and a calendar marked with their visits to our facilities.

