## General study plan

In total 12 subjects (with the aim of 10 subjects completing the study) will be recruited for the present project of which 50% (n=6) will be men and 50% will be women (n=6) between 18 and 40 years of age. Subjects will have a BMI above 18.5 and under 30 kg/m^2, will be nonsmokers and with no disease diagnosis.

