### 5-2 SAMPLE SIZE CALCULATION

As untargeted metabolomics is a data driven approach, which consists in detecting thousands of metabolites in biological samples with various analytical and inter-individual variability, it is not relevant to calculate a unique statistical power to determine the number of subjects. Nevertheless, previous studies showed that metabolomics allows identification of food intake biomarkers in controlled intervention studies with 4 to 20 volunteers

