#### **5-4 SUBJECT WITHDRAWAL CRITERIA**

Subjects may discontinue their participation in the study at any time.

The clinical Investigator may remove a subject, if, in his opinion, it is in the best interests of the subject.

A subject may be withdrawn from the study for any of the following reasons:

- Withdrawal of consent - any subject may withdraw from the study at any time
- Significant deviation from the protocol
- Lost of follow up
- Death
- Incidental illness
- Occurrence of a serious or considered serious adverse event or significant alteration in clinical and/or laboratory parameters. In these cases, appropriate actions will be taken. The sponsor will be notified immediately.

When the investigator had no news of the participant, he must have made every effort to contact him, to establish the reason for the discontinuation of treatment, and to suggest the participant to come to an end-of-study visit. If all these attempts to contact the participant failed, the investigator could then declare the participant “lost to follow-up”. The investigator should document all these attempts in the corresponding medical file. If a volunteer discontinues the study before the end of recruitment period, a new volunteer will be included with the same treatment. The investigator will record the reason(s) and the exact time of premature withdrawal of the study in the case report form. If more than one reason will be given, the investigator will indicate the main reason. The investigator will notify the sponsor of study withdrawals immediately using the page provided for this purpose in case report form by faxing to the study monitor.

In the case of withdrawal from the study due to a serious or non-serious adverse event, the investigator will make every effort to collect the information relating to the outcome of the event. If necessary, the information will be collected afterwards. This information will be recorded in that part of the case report form which concern adverse events. If the investigator cannot collect the information from a visit, he will collect it from the doctor ensuring the follow-up of the participant.

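### Random order is credited with controlling order and carry-over effects, but balance over periods is not required and the analysis has no period term or carry-over check

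*Protocol*

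**What the plan says.** Protocol section 4 describes the design as follows: "The present project is a randomized, controlled, crossover study with 12 subjects". It then concedes: "Limitations attributed to cross-over designs are possible order or carry-over effects". The reply given there is that "These effects will however be minimized due to a randomized intervention order". On allocation the same section says only: "Volunteers will be randomly assigned to a different food at each time point". The Summary and section 6-1 also speak of random order or random assignment. No visible text names a sequence list, blocks or a Latin square.

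The General study plan sets 6 men and 6 women, "with the aim of 10 subjects completing the study". Under section 5-4, when a volunteer leaves before recruitment ends, "a new volunteer will be included with the same treatment".

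Other sections hold the features that bear on carry-over: a washout of 3 to 10 days (section 4), two run-in days without banana or tomato before each test day (sections 6-1 and 6-4) and at least 7 days between visits (section 6-1). Blood at 0h and a first-void urine are collected before each test food.

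On analysis, protocol section 9 plans ANOVA with Benjamini-Hochberg (BH) correction plus multivariate methods. The SAP plans a Student t test with BH for urine and a one-way ANOVA over time points for plasma, each combined with PLS-DA-type models. None of these is described with a period, sequence or carry-over term.

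**The concern.** Two different problems are given one remedy that fully solves neither. Carry-over is limited by elapsed time and dietary restriction; random order only spreads whatever remains across the comparisons. Period effects are balanced by design only if each food falls equally often in each period. Unrestricted randomisation achieves that on average over hypothetical repetitions, not in the single allocation of 12 that the trial will use.

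The stake is a shared error. One allocation serves every ion. If banana falls later than control on average, each ion with a trend over periods is pushed according to its own trend, and BH does not remove a bias that many ions share. The urine contrast is the more exposed, because the SAP describes no baseline comparison for it. Carry-over would mostly act the other way: residue in a later control period shrinks the food-control contrast, and residue at 0h shrinks the rise on which plasma ions are selected. True markers could then be missed.

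**Working it through.** **Inputs from the documents.** 12 volunteers; 3 foods, so 3! = 6 orders; 6 men and 6 women; target of 10 completers. Two figures in the plan reproduce: 2 × 12 = 24 samples for banana plus control (SAP), and 1 day to Day 4 + 3 washout days + 3 days to the next Day 3 = 7 days between visits (section 6-1). The sample size itself cannot be re-derived, because section 5-2 holds that "it is not relevant to calculate a unique statistical power to determine the number of subjects".

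**Assumptions.** Each volunteer receives any of the six orders with probability 1/6. There is no food effect. The period trend is linear, in units of the SD of the paired banana-control difference. The test is a paired t test, two-sided 5%, 11 df. The SAP does not say whether its t test is paired.

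**Step 1: how uneven the allocation could be (exact).**
- Each order used exactly twice: 12!/(2^6 × 6^12) = 0.0034, or 0.34%.
- At least one order unused: 56.2%.
- Banana-before-control split of 9:3 or worse, either way: 2 × P(Binomial(12, 0.5) ≤ 3) = 14.6%.
- Banana-control period gap for one volunteer: ±1 in four orders and ±2 in two, so the variance is (4 × 1 + 2 × 4)/6 = 2. The mean over 12 has SD √(2/12) = 0.41 period.
- Absolute mean gap of at least 0.5 period: 26.5% with 12 volunteers and 32.0% with 10.
- Some food in the same period for all 12: 0.0017%.

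**Step 2: effect on a paired test (simulation).**

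| Drift per period (SD of paired difference) | Rejection, all allocations | Rejection given gap ≥ 0.5 | Same, food higher only |
|---|---|---|---|
| 0.1 | 5.0% | about 5.5% | 2.7% |
| 0.25 | 5.0% | about 7% | 3.5% |
| 0.5 | 5.1% | about 11% | 5.6% |
| 1 | 5.2% | about 17% | 8.6% |

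The last column should be read against 2.5%. It keeps only results in the direction the SAP requires; BH and VIP > 2 come on top and are not modelled.

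**Step 3: balanced orders.** With two volunteers per order, every food falls 4 times in every period and directly follows each other food 4 times, so the mean gap is 0. An unadjusted paired test is then conservative under drift, because the trend inflates the SD of the differences: it rejects 4.7%, 3.8%, 1.8% and 0.1% of the time at the four drifts above. At 10 completers exact balance is impossible, since 10 is divisible by neither 3 nor 6. Both facts call for a period term.

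**Step 4: price of the period term.** A three-food within-subject model has 36 observations. Error df are 36 − 12 volunteers − 2 food − 2 period = 20, against 22 without period. With 10 completers they are 30 − 10 − 2 − 2 = 16.

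**The case against.** A reader might infer that the orders are unbalanced. The documents do not say so: the method is unstated, a balanced list is not excluded, and the study-plan figure is not visible. Every percentage in Step 1 therefore depends on assuming simple randomisation.

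A reader might also take 11% or 17% as the trial's false-positive rate. They are not. They condition on the more uneven quarter or so of allocations and on drifts that no document supports; averaged over allocations the test holds its level, and small drifts barely move it. The SAP also applies direction, BH and VIP filters.

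The likely sources of drift are limited too. Samples are stored at −80°C, so instrument drift follows run order, which is not stated, rather than study period. Season differs mainly between volunteers, since section 6-4 gives 18 days to 5 weeks per person within a six-month study.

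Nor is carry-over left unprotected: the washout, run-in and 7-day spacing are real safeguards. No half-lives are given, so whether any carry-over remains cannot be judged. Finally, this is a discovery screen whose candidates go on to validation.

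All of this stands and limits the size of the point. It does not rescue the sentence in section 4, which rests on randomisation alone, and it does not supply the missing period term or the check of pre-dose samples.

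**Conclusion.** The point holds as a gap in design and analysis that is cheap to close, not as a demonstrated bias. Section 4 credits randomised order with a protection against carry-over that it cannot give and a period balance that it does not guarantee. The method of randomisation is not stated, balance is not required, and the analysis has no backstop.

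Under assumed simple randomisation, the chance of a banana-control gap of half a period or more is 26.5%. Given such a gap, a paired test rejects at about 5.5% to 17% over assumed drifts of 0.1 to 1 SD, before the SAP's filters. The title-level inference that food and period would be confounded goes too far: chance produces partial imbalance, and complete confounding is practically impossible. If a balanced list already exists, one sentence stating it settles the allocation half; the analysis half remains.

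**What to change.** - **Allocation (sections 4 and 6-1).** Allocate from a list that uses each of the six orders twice, once among the 6 men and once among the 6 women. This fits the planned numbers exactly.
- **Replacement (section 5-4).** Every volunteer takes all three foods, so "a new volunteer will be included with the same treatment" is ambiguous. Say that the replacement takes the withdrawn volunteer's order.
- **Section 4 claim.** Credit the washout and run-in for limiting carry-over, and the balanced orders for period effects.
- **SAP, univariate step.** Replace the per-ion two-group t test with a within-subject model with food and period terms, keeping BH.
- **SAP, exploratory check.** Compare 0h blood and first-void urine by preceding test food. Say that diet between periods limits its reading: section 6-1 allows the normal diet, which may include banana or tomato, while section 4 refers to following the dietary recommendations. Those two statements should be reconciled.

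If allocation has already been made, tabulate the realised orders by food and period and apply the two SAP changes.

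Cost: an allocation list, some rewording, a different per-ion model and 2 error df in the three-food model. No extra volunteers, visits or samples are needed, and the PLS-DA steps are unchanged, so they remain unadjusted for period.
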